7.3.1 Survival Follow Up

Once subject progresses or starts use of alternative antineoplastic therapy (for subjects who have not withdrawn consent), they will be contacted approximately q 12 weeks (\pm 2 weeks) for 1 year and then q 24 weeks (\pm 4 weeks) from the last dose of study drug by clinic visit or telephone to assess survival and the use of alternative antineoplastic therapy and stem cell transplant. Subjects will be contacted until: death, consent withdrawal, lost to follow up, or study termination, whichever comes first.

7.3.2 Missed Evaluations

Missed evaluations should be rescheduled and performed as close to the original scheduled date as possible. An exception is made when rescheduling becomes, in the opinion of the investigator, medically unnecessary or unsafe. In that case the missed evaluation should be abandoned.

Proprietary Information of MD Anderson

7.4 Description of Procedures

7.4.1 Medical History

The subject's medical history through review of the medical records and by interview will be collected and recorded. A disease history including date of initial diagnosis and baseline symptoms and severity should be recorded.

7.4.2 Physical Examination

The physical exam should include the general state of the subject, examination of the skin, eyes, ear, nose, throat, lungs, heart, abdomen, extremities, lymphatic system. Nervous system should be included if clinically indicated.

7.4.3 Vital signs

Vital signs including weight, blood pressure, heart rate, respiratory rate, and temperature will be recorded. Height will only be recorded during the screening phase, Visit 1.

7.4.4 ECOG PS

Table 6: Performance status definitions

Status	ECOG PS Definition
0	Fully active, able to carry on all pre-disease performance without restriction
1	Restricted in physically strenuous activity but ambulatory and able to carry out work of a light or sedentary nature (ie, light housework, office work)
2	Ambulatory and capable of all self-care, but unable to carry out any work activities. Up and about more than 50% of waking hours
3	Capable of only limited self-care, confined to bed or chair more than 50% of waking hours
4	Completely disabled. Cannot carry on any self-care. Totally confined to bed or chair
5	Dead

7.4.5 Concomitant Medications

All concomitant medications including over the counter medications and supplements should be recorded starting during the screening phase and continued through the treatment phase as well as up to 30 days after last study drug dose. Concomitant medications will be available in the electronic medical record.

7.4.6 Adverse Events

Only laboratory abnormalities which result in signs or symptoms that require intervention or follow up and are considered clinically significant should be recorded as AEs. See Section 10 for more details. All other AEs whether serious or non-serious will be entered in PDMS/CORE (the electronic case report form) from the time of signed and dated ICF up until 30 days after the last dose of study drugs. The Principal Investigator or designee will be responsible for assigning attribution to the study drugs.

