3.2 Endpoints

3.2.1 Primary Endpoint:

Proprietary Information of MD Anderson

Progression-free survival (PFS) at 2 years as assessed by the investigator

3.2.2 Secondary Endpoints:

Efficacy:

- Complete response rate ([CR], based on Cheson, Lugano classification 2014) at 120 weeks as assessed by the investigator
- Overall response rate (CR + partial response [PR]) based on Cheson, Lugano 2014 as assessed by the investigator
- Duration of response (DOR)
- Event free survival (EFS)
- Time to next anti-lymphoma treatment (TTNT)
- Overall survival (OS)

Safety:

- Frequency, severity, and relatedness of treatment-emergent adverse events (AEs)
- Frequency of treatment-emergent AEs requiring discontinuation of study drug or dose reductions

3.2.3 Exploratory Endpoints:

- Immunophenotyping of PBMCs to determine alteration in immune cell subsets
- Identification of signaling pathways or biomarkers that predict sensitivity or resistance by gene expression profiling
- Determination of alteration of cytokines and chemokines

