5.4 Dose Reduction, Delay and Discontinuation

Toxicity necessitating dose modification or delay is based on NCI CTCAE v 4.03 Toxicity Grade. The Principal Investigator will assess whether each AE is related or not to each of the study drugs. Events that are judged definitely, probably or possibly related are considered related AEs. Events that are considered unlikely or definitely not related are considered not related AEs. Factors to be taken into consideration include the temporal relationship between administration of study drug and the onset of the AE, other potential causes of the AE including the subject's underlying medical condition and concomitant medications, whether the AE is consistent with known AEs previously attributed to a study drug, whether the AE decreases or resolves upon withholding or reducing the dose of the study drug, or whether the AE recurs upon reintroduction of the study drug. AEs defined below (Sections 5.4.1), unless the Principal Investigator considers the event clearly unrelated to study drug, will be considered a toxicity that necessitates dose modification or delay.

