5.4.1 Toxicities Necessitating Dose Modification or Delay

Toxicities necessitating dose modification or delay will be defined as any non-hematologic or hematologic toxicity listed below. Study treatment should be discontinued in the event of a toxicity lasting more than 28 days despite appropriate medical management, unless reviewed and approved by the Principal Investigator. The action in Table 3 should be taken for the following toxicities:

Proprietary Information of MD Anderson

Non-hematologic toxicity will be defined as any of the following:

- Any unmanageable Grade 3 or 4 non-hematologic toxicity with failure to improve (< Grade 2) or recover to baseline within 14 days of withholding drug
- Grade 3 or 4 non-blistering rash that does not resolve to < Grade 2 within 14 days
- Any desquamating (blistering) rash
- Any grade Stevens-Johnson syndrome or toxic epidermal necrolysis
- Grade 3 or 4 thrombosis/embolism
- Grade 3 or 4 peripheral neuropathy which began or worsened while on study

Hematologic toxicity will be defined as any of the following:

- Grade 3 neutropenia with infection or fever (single temperature of > 38.3 °C, or with a sustained temperature of ≥ 38 °C lasting > 1 hour).
- Grade 4 neutropenia (ANC<500/µL) lasting > 7 days.
- Grade 4 thrombocytopenia (<25,000/µL)

The following action should be taken for any unmanageable toxicity that is consistent with the rules outlined above:

Table 3. Dose modification for toxicity

Toxicity Grade	Action to be Taken
Grade 3 neutropenia associated with fever (single temperature of > 38.3 °C, or with a sustained temperature of ≥ 38 °C lasting > 1 hour)	
• Hold lenalidomide and ibrutinib.• Follow CBC weekly.• If neutropenia has resolved to < Grade 2 prior to Day 21 of the current cycle, restart lenalidomide at next lower dose level, (see Table 5) and continue through the scheduled Day 21 of the current cycle. Otherwise, omit for remainder of cycle and reduce the dose of lenalidomide by 1 dose level at the start of the next cycle.
OR	
• Withhold ibrutinib until recovery to < Grade 2 or baseline; may restart at original dose level for the first occurrence. For subsequent occurrence, please refer to Table 4 for next lower dose level.• Withhold rituximab until recovery to < Grade 2 or baseline.• Omitted doses are not made up.• G-CSF may be used

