≥ Grade 4 thrombocytopenia	
• Hold lenalidomide and ibrutinib dose.• Follow CBC weekly.• If thrombocytopenia resolves to < Grade 2 prior to Day 21 of the current cycle, restart lenalidomide at next lower dose

Proprietary Information of MD Anderson

	
level and continue through the scheduled Day 21 of the current cycle. Otherwise, omit for remainder of cycle and reduce the dose of lenalidomide by 1 dose level at the start of the next cycle.
 
Withhold ibrutinib until recovery to < Grade 2 or baseline; may restart at original dose level for the first occurrence. For subsequent occurrence, please refer to Table 4 for next lower dose level.Withhold rituximab until recovery to < Grade 2 or baseline.Omitted doses are not made up.Hold prophylactic anti-coagulation including aspirin, if applicable.Restart prophylactic anti-coagulation and/or aspirin when platelet count is $\geq 50,000/\text{mm}^3$.
Non-blistering rash Grade ≥ 3	
If Grade ≥ 3, hold lenalidomide and ibrutinib dose. Follow weekly. If the toxicity resolves to < Grade 2 prior to Day 21 of the current cycle, restart lenalidomide at original dose level (for first occurrence) and continue through the scheduled Day 21 of the current cycle. Otherwise, omit for remainder of cycle.Omitted doses are not made up.For the second occurrence of Grade ≥ 3, hold lenalidomide, and follow weekly. If the toxicity resolves to \leq Grade 2 prior to Day 21 of the current cycle, restart lenalidomide at next lower dose level and continue through the scheduled Day 21 of the current cycle. Otherwise, omit for remainder of cycle and reduce the dose of lenalidomide by 1 dose level at the start of the next cycle. Omitted doses are not made up.Withhold ibrutinib until recovery to Grade ≤ 1 or baseline; may restart at original dose level for the first occurrence. For subsequent occurrence, please refer to Table 4 for next lower dose level.Treatment with 10mg of prednisone or equivalent for 10 days (with or without taper) and/ or antihistamines PO daily is recommended.If Grade ≥ 3 rash has not improved to at least Grade 1 within 14 days of drug being withheld and administration of 10mg of steroids and/or antihistamines daily, the subject will discontinue study treatment.

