9.1.2 Safety Monitoring

Proprietary Information of MD Anderson

The Principal Investigator or a physician designee will assess each subject to evaluate for potential new or worsening AEs as specified in the Trial Flow Chart, Appendix 13.1 and more frequently if clinically indicated. Adverse experiences will be graded and recorded throughout the study and during the follow-up period according to NCI CTCAE Version 4.03. Toxicities will be characterized in terms regarding seriousness, causality, toxicity grading, and action taken with regard to trial treatment. The study investigators and data coordinators are responsible for entering the data and safety for this study including causality. For both AEs and SAEs, the Investigator will provide a record of the start and stop dates of the event.

Safety data will be monitored by the Principal Investigator and in accordance with institutional policies. The Investigator will record the action taken with the study drugs as a result of an AE or SAE, as applicable (e.g., discontinuation, interruption, or reduction of study drugs, as appropriate) and report if concomitant and/or additional treatments were given for the event. AEs and SAEs will be reviewed on an ongoing basis to identify safety concerns.

For subjects with a history of Hepatitis B or C, standard of care monitoring for viral reactivation will be conducted. Subjects with a history of Hepatitis B will be required to undergo hepatitis B reactivation prophylaxis unless contraindicated.

All SAEs that have not resolved upon discontinuation of the subject's participation in the study must be followed until recovered, recovered with sequelae, not recovered or death (due to the SAE).

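### Section 7.4.6 makes symptoms a condition for recording a laboratory abnormality as an AE; this conflicts with 5.4 and Section 10 and, read literally, removes some dose-reducing toxicities from the safety endpoints

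*Combined protocol and SAP*

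**What the plan says.** Section 7.4.6 gives the recording rule: "Only laboratory abnormalities which result in signs or symptoms that require intervention or follow up and are considered clinically significant should be recorded as AEs". It then refers the reader to Section 10 for detail, without saying which text governs if the two differ.

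The safety endpoints in 3.2.2 are both built on AEs. One is the frequency, severity and relatedness of treatment-emergent AEs. The other is "Frequency of treatment-emergent AEs requiring discontinuation of study drug or dose reductions".

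Section 5.4 treats the listed dose-modifying toxicities as AEs. Its wording is "AEs defined below (Sections 5.4.1), unless the Principal Investigator considers the event clearly unrelated to study drug", and such events call for a dose change or delay. Section 5.4.1 lists Grade 4 thrombocytopenia by platelet count alone, and introduces Table 3 with "The following action should be taken for any unmanageable toxicity that is consistent with the rules outlined above".

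Section 10.1.1 allows an abnormal laboratory finding to be an AE. Section 10.2.1.2 asks for an AE when the investigator judges that a laboratory parameter has worsened from baseline to a clinically significant degree. It also says that non-serious toxicities are AEs and must be entered in the database.

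**The concern.** Staff cannot apply both rules to the same event. Under 7.4.6, an abnormal result without signs or symptoms is not recorded as an AE, however severe it is and whatever was done about it. Under 5.4 and Section 10, symptoms are not required.

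Safety and tolerability is a secondary objective, and both of its endpoints count only AEs. If 7.4.6 is followed, a toxicity that changed treatment can be absent from the very endpoint meant to count AEs that change treatment. If some staff follow 7.4.6 and others Section 10, the reported frequencies have no single definition. A reader could not tell which events were counted.

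**Working it through.** The plan states no figure on this point. The check is a comparison of texts, followed by one event traced through them.

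**Step 1: which texts set a symptom condition?**
- 7.4.6: yes. The abnormality must result in signs or symptoms.
- 5.4 and 5.4.1: no. The listed events are called AEs, and Grade 4 thrombocytopenia is defined by a count below 25,000/µL.
- 10.1.1: no. It also excludes one asymptomatic laboratory finding by name, treatment-related lymphocytosis. That exclusion would be unnecessary if asymptomatic findings were already outside AE recording.
- 10.2.1.2, on laboratory worsening: no. The test is clinical significance in the investigator's judgment.
- 10.2.1.2, on non-serious toxicities: no. They are AEs and are entered.

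**Step 2: trace one event.** Take a Grade 4 thrombocytopenia that causes no symptoms, meets no seriousness criterion, is unmanageable in the sense of 5.4.1, and is not judged clearly unrelated to study drug.
1. It is a 5.4.1 toxicity, so Table 3 applies and lenalidomide and ibrutinib are held.
2. Both branches of the Table 3 row lower lenalidomide. The first reads "If thrombocytopenia resolves to < Grade 2 prior to Day 21 of the current cycle, restart lenalidomide at next lower dose" level; the second reads "Otherwise, omit for remainder of cycle and reduce the dose of lenalidomide by 1 dose level at the start of the next cycle".
3. It is an AE under 5.4 and under the non-serious toxicity rule in 10.2.1.2. It is also one under the worsening rule in 10.2.1.2 if the investigator finds it clinically significant.
4. Under 7.4.6, read literally, it is not an AE, because it has produced no sign or symptom.
5. It is then absent from treatment-emergent AE frequency and from AEs requiring dose reduction.
6. Section 9.1.2 does not restore it: "The Investigator will record the action taken with the study drugs as a result of an AE or SAE, as applicable". With no AE entry, the reduction has no AE to attach to.

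**Step 3: what still shows the event.** Section 9.3.4 summarizes clinically significant abnormal laboratory values, and 9.3.1 summarizes the number of dose modifications. Neither feeds the two endpoints in 3.2.2.

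**Step 4: size.** Inputs: n = 60 planned patients (4.1), assuming all are treated and so belong to the safety population (9.2). If k patients are omitted, and none has another AE counted in the same percentage, that percentage falls by k/60:
- k = 1: 1/60 = 1.7 points
- k = 2: 2/60 = 3.3 points
- k = 3: 3/60 = 5.0 points

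These are upper limits. An omitted event in a patient who already counts through another AE changes the percentage by 0. The documents give no rate from which k could be predicted.

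**The case against.** The strongest reply is that 7.4.6 sends staff to Section 10, where 10.1.1 describes an abnormal laboratory finding as a kind of sign. On that view a platelet count needing action satisfies 7.4.6 by itself. This does not hold. If every abnormality were its own sign, the requirement that it result in one would restrict nothing, yet the sentence opens with a word of restriction. The reference to Section 10 gives further detail, not precedence.

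A second reply is that this event is unlikely to be missed, because several places point to recording it. That stands in part: many staff would record it. It does not give the endpoint a single definition.

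Several stronger readings are tempting and are not supported:
- **That every other AE passage contradicts 7.4.6.** Section 9.1.2 says how toxicities are described ("Toxicities will be characterized in terms regarding seriousness, causality, toxicity grading, and action taken with regard to trial treatment"), not which laboratory results are AEs. Footnote g of the flow chart assumes that some abnormal laboratory results are AEs, which 7.4.6 also allows. In 10.2.1.2, the worsening rule depends on the investigator's judgment and speaks of a corresponding clinical event. The thrombocytopenia example there applies when the cause is unknown. The sentence there against recording a laboratory value concerns the term to be used, and supports neither side.
- **That the safety information is lost.** The laboratory summary and the dose-modification count remain, and events meeting a seriousness criterion stay reportable under Section 10.
- **That the loss is large.** The Background reports neutropenia in the earlier lenalidomide-rituximab study as 25% grade 3 and 10% grade 4, with febrile neutropenia below 1%. A reader might take the gap as the share at risk of omission. But that was a two-drug regimen, the neutropenia was reported there as an adverse event, and non-febrile is not the same as asymptomatic.

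**Conclusion.** The concern holds as a conflict between recording rules with a definite, limited consequence. Section 7.4.6 is at odds with 5.4/5.4.1, 10.1.1 and 10.2.1.2, and no order of precedence is given. Read literally, it removes a non-serious, asymptomatic Grade 4 thrombocytopenia handled under Table 3 from both AE-based safety endpoints.

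The effect is at most 1.7 percentage points per omitted patient, on the assumptions that 60 patients are treated and that the patient has no other AE in the same percentage. The number of such patients cannot be estimated from the documents, and it depends on staff following 7.4.6 rather than Section 10.

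A reader might infer that the efficacy result or the safety stopping rule is compromised. Neither is. The primary endpoint is PFS at 2 years, and the rule in 9.6 counts treatment-related deaths and treatment discontinuations in cycles 1 and 2, not dose reductions.

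**What to change.** Reconcile 7.4.6 with 5.4 and Section 10 in about two sentences:
- Remove the condition that a laboratory abnormality must result in signs or symptoms.
- State that a laboratory abnormality is recorded as an AE regardless of symptoms if it is a clinically significant worsening from baseline, or if it is a 5.4.1 toxicity that leads to a Table 3 action.

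The second sentence should be limited in this way. Wording that covered every laboratory result leading to a dose change would sweep in lenalidomide dosing by creatinine clearance under Table 2. The text should say that Table 2 dosing for pre-existing renal impairment that has not worsened is not an AE, in line with 10.1.1.

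Optionally, 9.3.4 could add a table of each patient's worst CTCAE 4.03 grade on the scheduled hematology tests. Footnote g of the flow chart already requires laboratory safety measurements to be graded.

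The cost is somewhat more AE entries and toxicity rates that look less favourable. No dosing rule changes.

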7.4.7 CT, PET/CT and MRI Scans

A CT scan (with contrast unless contraindicated) of the neck, chest, abdomen and pelvis are required for disease assessment. A “diagnostic quality” combined PET/CT with IV and PO (or water) contrast is an acceptable alternative to CT scans. In addition, if independent CTs are performed, a PET can also be used to augment tumor assessment. In the case where a CT with contrast is contraindicated, an alternative would be an MRI of the chest, abdomen, and pelvis.

In general, follow-up assessments will be done by CT scans. PET-CT scan is encouraged and should be done at baseline and repeated to confirm complete remission and/or at treatment discontinuation, unless the subject's insurance will not cover a PET as part of standard of care. In this situation, CTs are acceptable alternatives. For lymphomas that are not FDG-avid at screening, PET does not need to be repeated in subsequent assessments.

7.4.8 Response Assessment

Response assessment will be completed by the Principal Investigator using Cheson 2014 Lugano Criteria. At screening, up to 6 target lesions will be selected and followed for the duration of the study. Information on extranodal involvement can also be recorded. The best ORR will be documented.

7.4.9 Hematology

Hematology studies must include a complete blood count (CBC) with differential. Coagulation studies performed at screening will include a PT and PTT.

7.4.10 Serum Chemistry

Chemistry must include electrolytes (sodium, potassium, chloride, bicarbonate), blood urea nitrogen, creatinine, glucose, calcium, alkaline phosphatase, ALT, AST, total bilirubin, albumin, total protein, LDH, β 2-microglobulin, and uric acid.

7.4.11 Coagulation

Coagulation studies performed at screening will include PT/INR and activated PTT.

7.4.12 Hepatitis Serologies

Proprietary Information of MD Anderson

Hepatitis serologies include Hepatitis C antibody, Hepatitis B surface antigen, Hepatitis B core antibody. For patients with a positive Hepatitis C antibody, Hepatitis C viral PCR should be performed to evaluate for active infection.

7.4.13 HIV Serologies

HIV serologies include antibodies to HIV 1 and 2.

7.4.14 Creatinine Clearance

Determination of creatinine clearance using the modified Cockcroft-Gault estimate (utilizing actual body weight) should be calculated during the Screening phase, C1D1, C1D8, C1D15, C1D22, C2D1, C2D15 and at the start of each subsequent cycle to determine dose of lenalidomide (Table 2).

7.4.15 Pregnancy Test

During screening, two serum pregnancy tests will be required for women of childbearing potential. Females of childbearing potential are defined as: all females who are menstruating, amenorrheic from previous treatments, under 50 years of age, and/or perimenopausal, and do not qualify for the females not of reproductive potential category.

Females not of reproductive potential are defined as: females who have been in natural menopause for at least 24 consecutive months, or who have had a hysterectomy and/or bilateral oophorectomy, or female children who have not started menstruating and will not be required to undergo pregnancy testing. Females of reproductive potential must also adhere to the scheduled pregnancy testing as required in the Revlimid REMS® program, Appendix 13.6.

Urine pregnancy tests should be performed as clinically indicated for women of childbearing potential.

